### **6.3.13.2 Occurrence of Relapse**

The occurrence of Relapse, as defined in Section 6.1.5.4, during the tapering or follow-up period will be summarized descriptively by calculating the proportion of patients with ITI success who reaches the criteria for relapse. The TPFAS analysis set will be used.

In patients who are relapsing, the time between ITI success and the relapse will also be summarized descriptively.

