### **6.2 Secondary objectives**

To describe time to tolerization (i.e. ITI success) of ITI performed with rFVIIIFc within a timeframe of 60 weeks in patients who failed previous attempts at tolerization including use of immunosuppressants.

To describe the relapse rate over a 48-week period following successful ITI performed with rFVIIIFc.

To describe the intercurrent bleeding during ITI and during the 48-week period after successful ITI performed with rFVIIIFc.

To describe safety and tolerability of rFVIIIFc when used for ITI.

To describe the impact of ITI treatment with rFVIIIFc on health economy.

To describe adherence of rFVIIIFc when used for ITI.

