**9.3.4.2      Occurrence of relapse**

Occurrence of relapse will be summarized descriptively by calculating the proportion of patients with ITI success who reaches the criteria for relapse. The TPFAS set will be used for this analysis.

Time to relapse will be defined as the duration between the time of ITI success and time of relapse. Time to relapse will be summarized descriptively among those who relapsed.

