**6.2 *Analysis Populations***

The final assignment of the patients to the different analysis populations will be made during the Data Review Meeting (DRM) before database lock and statistical analysis, based upon the criteria described in this section. In general, it is not planned to exclude any patient from any analysis set, as long as they reach each period respectively.

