**PAREXEL International**  
**Statistical Analysis Plan**

### **6.2.2 Tapering Period Full Analysis Set**

The tapering period full analysis set (TPFAS) will include all patients who achieve ITI Success and enter the tapering period of the study. All analyses describing efficacy and safety during this period will be based on this analysis set. In addition, some of the analyses (e.g. bleeding and hospitalization) combine the tapering period and the follow-up period (described in Section 6.2) into a longer, 48-week follow-up period. The TPFAS will be used for these analyses as well.

The tapering period is defined to start at the visit after confirmed ITI success.

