## PAREXEL International

### Statistical Analysis Plan

Prognostic factors for ITI success will be summarized stratified by ITI outcome. Prognostic factors to consider include; historical peak inhibitor titer, pre-ITI inhibitor titer, factor VIII genotype, peak inhibitor titer on ITI, number of previous ITI attempts, time between inhibitor development and start of ITI. In this summary, patients will be included according the best ITI outcome they achieve (partial success is not also counted as failure and complete success is not also counted as partial success). The following categorical variables will be derived for this summary:

- Historical Peak Inhibitor Titer <200 BU (yes/no)
- Pre-ITI Inhibitor Titer <10 BU (yes/no)
- >5 Years between Diagnosis of Inhibitor and Start of ITI (yes/no)

The ITIFAS analysis set will be used for this analysis.

A figure will be presented showing the number and percentages of patients by ITI outcome versus time (up to Week 60, patients will be counted for each time point after their ITI outcome has been determined, regardless of discontinuation or relapse).

In addition, a treatment outcome listing will be produced, displaying for each patient:

- Outcome (ITI success, partial success, failure or not determinable [if withdrawal due to other reasons prior to 60 weeks])
- Study day each of the success criteria was met (blank if not met)
- Relapse (no or relapse criteria met)
- Days after ITI success to relapse

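### The 48-week relapse figure is a crude proportion with no allowance for successes who leave early; add a Kaplan-Meier estimate beside it

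*SAP*

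**What the plan says.** The objective in protocol 6.2 is "To describe the relapse rate over a 48-week period following successful ITI performed with rFVIIIFc". The 48 weeks are the 16-week tapering period plus the 32-week follow-up period.

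Protocol 9.3.4.2 and SAP 6.3.13.2 give the same two summaries. The first is a proportion: "Occurrence of relapse will be summarized descriptively by calculating the proportion of patients with ITI success who reaches the criteria for relapse" in the protocol and, in the SAP, "calculating the proportion of patients with ITI success who reaches the criteria for relapse". The second is time to relapse, limited to those who relapse: "Time to relapse will be summarized descriptively among those who relapsed" in the protocol and, in the SAP, "In patients who are relapsing, the time between ITI success and the relapse will also be summarized descriptively".

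The denominator is the TPFAS, which "will include all patients who achieve ITI Success and enter the tapering period of the study" (SAP 6.2.2). SAP 6.2 adds that "it is not planned to exclude any patient from any analysis set, as long as they reach each period respectively". In the treatment outcome listing of SAP 6.3.12.1 the relapse entry has two states: "Relapse (no or relapse criteria met". SAP 6.3.5 rules out imputation. Section 8 of the SAP plans a relapse summary (Table 14.2.1.7) and a descriptive time to relapse (Table 14.2.1.8). The Kaplan-Meier plots in section 9 cover ITI success, negative titer and incremental recovery (IR), but not relapse.

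**The concern.** A proportion over a fixed window answers the objective directly only if every patient without the event is observed to the end of the window. Here that is not assured. Protocol 7.3.3 lists reasons for withdrawal that can arise after success, such as major surgery, emicizumab, immunosuppressants or withdrawn consent, and SAP 6.3.8 plans to count withdrawals within each period. Relapse also needs two consecutive assessments (SAP 6.1.5.4), so a patient who leaves after a first positive result but before the repeat has not met the criteria either.

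The plan allows for unequal follow-up elsewhere. Bleeding over the same 48 weeks, in the same set, is annualised for that reason (protocol 9.3.4.4, SAP 6.3.13.4). Time to ITI success uses Kaplan-Meier with censoring (SAP 6.3.13.1). Relapse gets neither. At stake is the figure that readers will take as the durability of tolerance, in a set smaller than the 20 patients planned unless every one succeeds.

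**Working it through.** **Inputs.** From the documents: window 16 + 32 = 48 weeks; 20 patients planned with no formal sample size calculation; denominator TPFAS; no exclusion or censoring rule for relapse. The documents give no success, relapse or post-success withdrawal rate, so all counts and rates below are assumed. The plan has no relapse figure to reproduce.

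**Formulas.** With n successes, r relapses and w successes who leave early without relapse:
- crude = r/n
- Kaplan-Meier relapse by week 48 = 1 − product over relapse times of (1 − relapses ÷ number at risk)
- upper bound = (r + w)/n, if every early leaver had relapsed by week 48

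Whatever the reason for leaving, the true 48-week proportion in the set lies between r/n and (r + w)/n. The crude figure is therefore the lower end of that range.

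**Worked sets.**

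| Successes | Relapses (week) | Early exits (week) | Crude | Kaplan-Meier | Upper bound |
|---|---|---|---|---|---|
| 7 | 1 (20) | 2 (before 10) | 1/7 = 14% | 1 − 4/5 = 20% | 3/7 = 43% |
| 6 | 1 | 1 (before the relapse) | 1/6 = 17% | 1 − 4/5 = 20% | 2/6 = 33% |
| 10 | 2 (12, 28) | 2 (8) | 2/10 = 20% | 1 − (7/8)(6/7) = 25% | 4/10 = 40% |
| 10 | 2 (12, 28) | 2 (20) | 20% | 1 − (9/10)(6/7) = 22.9% | 40% |
| 6 | 2 (12, 28) | 2 (8) | 2/6 = 33.3% | 1 − (3/4)(2/3) = 50% | 4/6 = 66.7% |
| 12 | 1 (28) | 2 (8) | 1/12 = 8.3% | 1 − 9/10 = 10% | 3/12 = 25% |
| 10 | 1 (12) | 2 (20) | 10% | 1 − 9/10 = 10% | 3/10 = 30% |
| 10 | 2 (12, 28) | 0 | 20% | 20% | 20% |

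The last two rows show where crude and Kaplan-Meier agree: exits only after the last relapse, or no exits.

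**Expected size.** Let p be the true 48-week relapse risk and q the probability of withdrawal by week 48. Assume exponential times and exit independent of relapse. With a = −ln(1 − p) and b = −ln(1 − q), the expected crude proportion is a/(a + b) × [1 − (1 − p)(1 − q)].

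For p = 0.30 and q = 0.10: a = 0.357, b = 0.105, so 0.772 × (1 − 0.63) = 0.286.

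| True risk | q = 10% | q = 20% | q = 30% |
|---|---|---|---|
| 30% | 28.6% | 27.1% | 25.5% |
| 15% | 14.3% | 13.5% | 12.7% |

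The shortfall is 1.4 to 4.5 points for a true 30%, and 0.7 to 2.3 points for a true 15%.

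**The case against.** A reader might infer that the SAP declares withdrawn patients relapse-free to week 48. It does not. It reports an observed count; the effect follows from the denominator, the two-state listing and the absence of a rule. SAP 6.3.1 does make missing values a separate category, but nothing links that to relapse status. The protocol names the endpoint as occurrence of relapse, for which a proportion is a natural measure.

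A reader might also infer that any surgery, or any use of another FVIII product, forces exit. Protocol 7.3.3 withdraws for major surgery only and allows one emergency or accidental use of another product.

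Nor is the time-to-relapse summary biased as described. Both documents say that it covers relapsers, and it is correct for them. It would mislead only if read as durability among all successes.

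Follow-up can largely be reconstructed. Withdrawals are tabulated by period with reasons (SAP 6.3.8), and titers and IR are listed for each patient. Protocol 7.3.3 asks that withdrawn patients be examined where possible, preferably on the end of treatment schedule, so relapse status at exit will often be known. The endpoint is descriptive, and precision is poor anyway: for 1/7 the exact 95% interval is about 0.4% to 58%, so 14% and 20% cannot be told apart.

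Kaplan-Meier brings its own difficulties. It assumes that exit is unrelated to relapse, yet leaving for emicizumab or another FVIII product could be related. The final visit falls at week 48 ± 2 weeks, so censoring everyone at the last assessment can go badly wrong. With ten successes, nine completers last seen at weeks 46 to 47 and one relapse dated week 48, only one patient is at risk. The estimate is then 1 − 0/1 = 100%, against a crude 1/10.

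These points limit the concern and shape the remedy. They do not remove the gap: no planned summary table allows for incomplete follow-up in the relapse figure.

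**Conclusion.** The concern holds as a minor point. The planned proportion is a lower limit for 48-week relapse, and it understates relapse when non-relapsing successes leave before later relapses occur. In expectation the shortfall is about 1 to 5 points for a true 30% with 10% to 30% withdrawal, if exit is unrelated to relapse. It can be larger in a single small set, and it is zero with no early exits. All of these sizes rest on assumed rates and counts. If exit is related to relapse, Kaplan-Meier may also be wrong, which is why the range up to (r + w)/n should be shown with it. The point does not affect the primary endpoint.

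**What to change.** In SAP 6.3.13.2, keep the crude proportion and the relapsers-only summary, and add:

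- A Kaplan-Meier estimate of time from ITI success to relapse on the TPFAS, read at the nominal week 48 visit.
- Censoring of early withdrawals without relapse at their last inhibitor/IR assessment. Patients who complete the week 48 (± 2 weeks) visit without relapse count as followed to week 48. In the ten-patient example above, this gives 1 − 9/10 = 10%, equal to the crude figure, as it should be with no early exits.
- The number of successes followed to week 48 and the number who left earlier without relapse.
- A sensitivity count that treats those early exits as relapses.

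Confidence limits are optional. SAP 6.3.3 says that none will be presented, so including them would need an explicit exception.

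The cost is one table. The LIFETEST code in SAP 6.3.13.1 can be adapted once the censoring variable follows the rule above, and no new data are needed. The downside is an imprecise estimate when successes are few; the counts of complete and incomplete follow-up will then be the more informative part.

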### **6.3.13.3 Number of Bleedings during ITI treatment**

Bleeding episodes during ITI treatment will be summarized per month as follows:

- Number of bleeding episodes (also shown for the entire treatment period)

**PAREXEL International**  
**Statistical Analysis Plan**

- Number and percentage of patients experiencing at least one bleeding episode (also shown for the entire treatment period)
- Number and percentage of patients and total number of bleeding episodes for spontaneous and traumatic bleedings (also shown for the entire treatment period)
- Number and percentage of patients and total number of bleeding episodes by anatomical location (also shown for the entire treatment period)
- Patient bleeding event rate: total bleeds per month (minimum, maximum, median, mean, Q1, Q3 standard deviation). Patients without bleeding are included as a zero count

For the purpose of this analysis, each month is defined as Number of Days/30. Bleeding episodes are counted in the month based on start date. Study Day 1 is the first day of the first month.

In addition, annualized bleeding event rates (ABR) will be displayed, defined for each patient as follows:

$$ABR = ev \frac{365.25}{\text{length of ITI period in days}}$$

Here, ev is number of events for the specific patient.

The ITIFAS analysis set will be used for this analysis.

All bleeding episodes during the study (regardless of period) will be listed individually. The period in which the bleeding event occurred (based on start date) will be indicated in this listing.

An additional listing will show the total number of bleeding episodes per month and location and total for each patient in the ITI Period.

#### **6.3.13.4 Bleeding Rate During 48-week Follow-up Period**

Descriptive statistics for the bleeding episodes during the 48-week follow-up period (including tapering period) will be displayed using the TPFAS analysis set.

In addition, annualized bleeding event rates (ABR) will be displayed, defined for each patient as follows:

$$ABR = ev \frac{365.25}{\text{length of follow-up period in days}}$$

Here, ev is number of events for the specific patient.

**PAREXEL International**  
**Statistical Analysis Plan**

#### **6.3.13.5 Consumption**

The total study drug consumption as well as the total consumption of bypassing agents will be calculated for each patient by period and listed using the respective period analysis sets. Consumption will also be summarized by period (in the standard absolute dose and dose/kg for the respective product) using the ITIFAS. The consumption for 'other' (per eCRF) bypassing agents will only be summarized, if at least 3 subjects took the specific product.

An additional listing will show the consumption of rFVIIIFc, Novoseven® and FEIBA® in the ITI period.

For the ITI Period, the Tapering Period and the Follow-up Period annualized consumption (AC) will also be calculated and summarized:

$$AC = CP \frac{365.25}{\text{length of period in days}}$$

Here, CP is the total consumption of the period in that study.

#### **6.3.13.6 Number of Days Missed School or Work During ITI Treatment**

The number of days missed during ITI treatment will be listed and summarized descriptively using the ITIFAS set. The listing will also include later periods. The total number of missed days in the ITI Period will be annualized as described in Section 6.3.13.5.

#### **6.3.13.7 Number of Days Missed School or Work During a 48-week Period Following Successful ITI Treatment**

The number of days missed during the 48-week follow-up period (including tapering period) will be summarized descriptively using the TPFAS set. An annualized number of days (ADM) missed will also be displayed, calculated as described in Section 6.3.13.5.

#### **6.3.13.8 Number of Hospitalizations During ITI Treatment**

The ITIFAS set will be used to list and summarize the number and total length of hospitalizations during the ITI treatment. This summary will be presented together with that of number of days missed described above. Descriptive statistics for the number of days hospitalized will be calculated and summarized in two different ways:

1. Patients who were not hospitalized are counted as having been hospitalized for zero days

**PAREXEL International**  
**Statistical Analysis Plan**

2. Patients who were not hospitalized are considered missing for the calculation of days hospitalized

The listing will also include later periods. The total number of hospitalizations in the ITI Period will be annualized as described in Section 6.3.13.5.

**6.3.13.9 Number of Hospitalizations During a 48-week Period Following Successful ITI Treatment**

The TPFAS set will be used to summarize the number and total length of hospitalizations during the ITI treatment. Both number and total length will also be annualized in the same manner as described in Section 6.3.13.4. This summary will be presented together with that of number of days missed school or work as described above.

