**9.3.4.7      Number of days missed school or work during a 48-week period**

**following successful  
ITI treatment**

Number of days missed school or work during the 48-week period following ITI treatment will be summarized descriptively. TPFAS analysis set will be used for this analysis.

**9.3.4.8      Number of  
                  hospitalizations  
                  during ITI  
                  treatment**

Number of hospitalizations during ITI treatment will be summarized descriptively. The ITIFAS analysis set will be used for this analysis.

**9.3.4.9      Number of  
                  hospitalizations  
                  during a 48-week  
                  period following  
                  successful ITI  
                  treatment**

Number of hospitalizations during the 48-week period following ITI treatment will be summarized descriptively. TPFAS analysis set will be used for this analysis.

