**6.1.5.4 Relapse**

Relapse in the tapering or follow-up period is defined as the occurrence of any of the following (with or without clinical symptoms) after complete ITI success:

1. Positive inhibitor ( $\geq 0.6$  BU/mL), on two consecutive assessments performed within 2-4 weeks  
 AND  
 2. An  $IR \leq 66\%$  of the expected IR, on two consecutive assessments performed within 2-4 weeks

For relapse the date at which relapse criteria was met will be recorded.

The time in days between relapse and ITI success will be derived, as the difference between the two dates.

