**PAREXEL International**  
**Statistical Analysis Plan**

### **6.3.8 Disposition**

Disposition data will be displayed using the ITIFAS.

The patient disposition will be summarized as follows:

- Number of patients dosed.
- Number of patients who completed each period.
- Number of patients who withdrew within each period, including reason of withdrawal.
- Number of patients who were discontinued due to not achieving ITI success in the ITI period by unfulfilled success criteria (see Section 6.1.5.3).
- Number of patients who completed the end of treatment visit.
- Number of patients who were discontinued due to relapse in the tapering period.
- Number of patients assigned to each analysis population.

Date of informed consent, withdrawals and the assignment of patients to the different analysis populations will also all be listed.

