**PAREXEL International**  
**Statistical Analysis Plan**

**Table 14.2.3.1** Summary of rFVIIIIFc Consumption by Period (ITIFAS)

**Table 14.2.3.2** Summary of Bypassing Agent Consumption by Period (ITIFAS)

**Table 14.2.3.3** Summary of Hospitalizations and Days Missed at School or Work During ITI Treatment (ITIFAS)

**Table 14.2.3.4** Summary of Hospitalizations and Days Missed at School or Work During 48-week Follow-up Period (TPFAS)

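### SAP 6.3.13.9 contradicts itself on the window for the post-success hospitalization endpoint; as a minor companion point, the relapse row in SAP 6.3.8 is incomplete

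*SAP*

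**What the plan says.** SAP 6.3.13.9 is headed "Number of Hospitalizations During a 48-week Period Following Successful ITI Treatment". Its first sentence sets the analysis set and the count: "The TPFAS set will be used to summarize the number and total length of hospitalizations during the ITI treatment". Its second sets the rate: "Both number and total length will also be annualized in the same manner as described in Section 6.3.13.4". SAP 6.3.13.4 multiplies events by 365.25 and divides by the length of follow-up in days. It introduces that follow-up as the 48-week period with tapering included.

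Other places give the window as follows:
- Protocol 9.3.4.9: "Number of hospitalizations during the 48-week period following ITI treatment will be summarized descriptively", on the TPFAS. Protocol 6.2.1 lists the endpoint in the same terms.
- SAP 6.2.2: "some of the analyses (e.g. bleeding and hospitalization) combine the tapering period and the follow-up period", forming a 48-week period analysed on the TPFAS.
- SAP Section 8: Table 14.2.3.4 is titled for the 48-week follow-up period on the TPFAS. Hospitalizations during ITI have their own table, 14.2.3.3, on the ITIFAS.
- SAP 6.3.13.7, on days missed from school or work, uses the 48-week follow-up including tapering. Its results share a table with those of 6.3.13.9.

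On disposition, the only relapse row in SAP 6.3.8 is "Number of patients who were discontinued due to relapse in the tapering period". SAP 6.1.5.4 defines relapse over both periods: "Relapse in the tapering or follow-up period is defined as the occurrence of any of the following". Under Protocol 7.1.4 and footnote a of Protocol Table 2, a patient who relapses in follow-up also goes to the end of treatment visit.

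**The concern.** The SAP introduces itself as the programming specification for the tables, and the sentence at issue is the only one in 6.3.13.9 that says which stays to count. It repeats the period named in 6.3.13.8, the ITI section, with the analysis set changed. Taken at its word, it pairs a numerator from before success with a divisor from after success.

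Two things would follow. Table 14.2.3.4 would show days missed after success beside hospitalizations before success. And the endpoint itself, hospital use once tolerance has been reached, would not be summarized. Individual stays would survive in the hospitalization listing, which covers later periods, and as SAEs, but their number and length per patient would not be tabulated for the post-success window.

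The disposition row raises a smaller question of the same kind. Relapse is not among the withdrawal reasons in Protocol 7.3.3, so the row for withdrawals by period and reason is not assured to pick up a patient who leaves for relapse in follow-up.

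**Working it through.** **Window.** SAP Section 2 gives an ITI period of at most 60 weeks, tapering of 16 weeks and follow-up of 32 weeks. 16 + 32 = 48 weeks, which reproduces the plan's figure. 48 × 7 = 336 days; 60 × 7 = 420 days.

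**Literal rule against intended rule.** For one patient let H be the number of stays (or days in hospital), D the period length in days and r the true annual rate.
- Intended: H(post) × 365.25 / D(post), with expectation r(post).
- Literal: H(ITI) × 365.25 / D(post), with expectation r(ITI) × D(ITI) / D(post).
- Ratio of literal to intended: [r(ITI) / r(post)] × [D(ITI) / D(post)].

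**Equal true rates, full 48 weeks of follow-up.** The first factor is 1 and the ratio is D(ITI) / 336.
- 60 weeks (document maximum): 420 / 336 = 1.25.
- 20 weeks (assumed): 140 / 336 = 0.42.
- 12, 24, 36 and 48 weeks (assumed): 0.25, 0.50, 0.75 and 1.00.

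The value of 1.00 at 48 weeks is a coincidence of lengths; the stays would still come from the wrong period.

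**Unequal rates.** The ratio then also carries r(ITI) / r(post), for which the documents give no figure. As an invented example, a patient with two stays during ITI and none afterwards would be reported at 2 × 365.25 / 336 = 2.17 per year, when the intended value is 0.

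**After the correction.** Numerator and divisor cover the same days: 336 / 336 = 1.00.

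**Disposition row.** Tapering is 16 / 48 = 33% of the post-success window, so 32 / 48 = 67% of that time has no relapse row. Of the eight scheduled visits after tapering initiation (weeks 2, 4, 8, 12, 16, 28, 40 and 48), three fall after week 16. These are shares of time and visits, not of relapses. If the relapse hazard were constant and the 48-week risk were p (both assumed), the share of relapses falling in follow-up would be 1 − [1 − (1 − p)^(16/48)] / p. That is 66% for p = 10% and 59% for p = 50%.

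**The case against.** The strongest reply is that nobody would be misled. One phrase is contradicted by its own heading, by the annualization rule in the same paragraph, by SAP 6.2.2, by the table title and by the protocol. A separate ITI table already exists, and the mismatch between numerator and divisor is itself a sign of carried-over wording. The hospitalization listing would let a wrong count be traced. This stands as to intent: a reader might infer that the SAP deliberately moved the endpoint into the ITI period, and the documents do not support that. It does not remove the need to correct the one sentence that specifies the count.

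A reader might also take the divisor to be the 32-week follow-up period alone. SAP 6.3.13.4 describes its period as 48 weeks with tapering included, so no figure here uses the shorter divisor. Nor should the ITI period of these patients be called inhibitor-positive throughout: to enter the TPFAS they must first meet the negative-titer, recovery and half-life criteria, so part of their ITI time is inhibitor-negative.

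On disposition, a reader might infer that relapses in follow-up are hidden or that a second result comes out wrong. Neither follows. The row is correct as labelled. Relapse in either period is analysed in SAP 6.3.13.2 and Tables 14.2.1.7 and 14.2.1.8, shown for each patient in the treatment outcome listing, and captured as an SAE and tabulated by period. That a follow-up relapser would be shown as a completer is not established either, because the SAP does not define a completer that way. What remains is that such a patient has no assured row of his own in the disposition table.

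**Conclusion.** The point holds as an internal contradiction in a programming instruction for a named secondary endpoint, with a clear intended reading. If the sentence were followed literally, the annualized result would be off by ITI length / 336 days, for example 1.25 at the 60-week maximum or 0.42 at an assumed 20 weeks. Those factors rest on equal true rates before and after success and on a full 48 weeks of follow-up. Post-success hospitalizations would also lose their summary. The harm arises only if the phrase is programmed against the heading and the table title.

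The disposition point is minor: the table is incomplete, not wrong, and the 67% describes one row's coverage of time, not relapse reporting. Neither point touches the primary endpoint, the relapse endpoint or any inference, since the study plans no tests and no confidence intervals. The hospitalization sentence should be corrected; the disposition row is worth extending at the same time.

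**What to change.** In SAP 6.3.13.9, replace the reference to the ITI treatment in the first sentence with the 48-week follow-up period including tapering, as SAP 6.3.13.7 already has it. State that the annualization divides by the patient's length of that same combined period.

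In SAP 6.3.8, extend the relapse row to patients discontinued due to relapse in the tapering or follow-up period, shown by period.

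The cost is two SAP sentences and one more line in the disposition table. No new data are needed, because hospitalization start and end dates and the relapse date are already recorded, and the title of Table 14.2.3.4 stays as it is.
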